- To determine the magnitude of mental disorders among persons affected by leprosy/BU in Southern Nigeria.
- 2. To determine the impact of a community-oriented, holistic approach on mental health status (depression and generalized anxiety disorder (GAD)) of persons affected by leprosy or BU.
- 3. To determine the impact of a community-oriented, holistic approach on quality of life of persons affected by leprosy or BU.
- 4. To determine the impact of a community-oriented, holistic approach on social participation of persons affected by leprosy or BU.
- 5. To determine the effect of socio-demographic variables on mental health status (depression and GAD) status of persons affected by leprosy or BU.
- 6. To determine the effect of physical impairment on mental health status (depression and GAD) of persons affected by leprosy/BU.
- 7. To determine the impact of a community-oriented, holistic approach on access to and utilization of mental health services and number of referrals for mental health care within all the levels of care.

Methodology

Nigeria, a West African country of nearly 200 million people is the most populous country in Africa. The country is divided into 36 States in 6 geopolitical zones and a Federal Capital Territory (FCT). Each state is divided into Local Government Areas (LGAs), which represent the third administrative level of governance. Altogether, there are 774 LGAs. The NTBLCP under the Federal Ministry of Health was inaugurated in 1988. The NTBLCP was initially responsible for Tuberculosis and Leprosy control but later added Buruli ulcer to its portfolio. At the turn of the century and up to 2007, Nigeria notified about 5,000 new leprosy cases annually. [17] Case notification declined steadily to 2687, 2447 and 2095 respectively in the last 3 years. Proportion of cases with visible deformities had remained high at 14-15%. Child and female proportion stood largely unchanged at 9% and 41% respectively. Despite achieving the WHO leprosy elimination target of less than 1 per 10,000 population in 1998, there continues to be pockets of high endemicity in some States and LGAs across the country.

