In 2007, a manual for organizing and running self-care groups (SCG) was adopted by the NTBLCP. [18] Despite the fact that an evaluation commissioned by the Netherlands Leprosy Relief found that 'the self-care groups have made huge impact with such outcomes as less ulcers, improved hygiene, higher self-esteem and better contacts with the community', self-care groups were not systematically set up and followed-up in Nigeria. The number of persons living with leprosy/BU-related disabilities is unknown. These data are not tracked by the national programme. However, the report of a national programme review conducted in 2015, put the estimated number of persons living with leprosy-related disabilities at 30,000. Levels of awareness of leprosy and BU remain remarkably low in many parts of the country. A survey of medical students and Doctors conducted in 2013 in south-east Nigeria showed poor knowledge of leprosy. [19] A national NTD mapping published in 2016, [20] shows that BU and leprosy are co-endemic in many states in both Northern and Southern Nigeria. This presents opportunities for integrated programming for management and control of these diseases. While adequate chemotherapy and appropriate adjuvant surgery were provided, little or no attention was given to the mental health of the BU and leprosy patients. Persons with leprosy and BU related disabilities are faced with varying degrees of stigma and discrimination which predispose them to mental health problems especially depression and

anxiety. Anecdotal evidence indicates that the level of stigma is far higher in Southern Nigeria than in the north.

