- Prevalence of mental disorders among persons affected by Leprosy/BU using PHQ-9 as screening tool for depression and GAD-7 (see annex for tools) to screen for GAD.
- Attitude of community leaders towards leprosy/BU patients using SDS and FGD/KII.
- Stigma perception among persons affected by leprosy/BU using SARI Stigma scale
- Quality of life and mental well-being of persons affected by leprosy/ BU using WHOQOL-BREF and WEMWBS.
- Perception of healthcare workers on mental well-being of leprosy/BU patients using FGD/KII.

The study and control groups will be compared after intervention to determine change in mental health status, quality of life and social participation of study participants.

Data quality will be guaranteed by:

- Training and supervision of research assistants
- Double transcription of voice recordings of KIIs and FGDs

Validation of study tools

Prior to field work, a short validation will be done to validate the WEMWBS tool in all relevant study sites in Nigeria.

This involves:

- Translation/back-translation of tool in Pidgin English, Igbo and Efik languages
- Conduct interviews to ascertain how well tool is understood (interpretability).
- Several rounds of translation/back-translation with 5-10 persons.

• Further validation will be done during field work.

Recruitment

To recruit study participants, first, names and contact details of leprosy or BU patients will be obtained from LGA Leprosy and Buruli ulcer Treatment Registers, respectively. Eligible persons will be contacted by phone calls through the LGA Tuberculosis and Leprosy Supervisors (LGTBLS) and invited for orientation meeting on a scheduled date. Newly detected, eligible leprosy or BU patients registered for treatment at the health facilities during intervention will also be evaluated for depression and GAD by healthcare workers using the research tools and thereafter introduced to nearby SHGs. All leprosy/BU patients who are eligible regardless of mental health status will be enrolled into SHGs up to one year before end of intervention. However, patients who come after the deadline will join the SHGs and receive appropriate services, but not included in final research analysis. All suspected cases of BU or leprosy found by community leaders or members of SHGs will be referred to health workers for diagnosis.

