Two research assistants per LGA comprising members of the selected communities will be trained for one day for data collection using the interviewer administered questionnaire. The research assistants must have attained at least secondary education. They will be trained on privacy and confidentiality before the study begins. The researchers will conduct the FGDs and KIIs. Interviewers will be trained on confidentiality procedures and undertake to ensure confidentiality as part of their engagement agreement.

A secured box will be made available in German Leprosy and TB Relief Association head office for the safe storage of the questionnaires and other materials related to the research. The recordings used for FGDs and KIIs will be transcribed immediately after the interview. English, Pidgin English, Efik or Igbo languages will be used to conduct FGDs and the discussions will take place in secluded areas of the selected communities like public primary schools and town halls.

Data entry and analysis for (quantitative data collection method) will be done using IBM Statistical Package for Social Sciences (SPSS) statistical software version 25. Categorical variables among the study and control groups will be compared using Chi square test of statistical significance while continuous variables will be compared using Student t test. In between group comparisons (like study group before and after intervention) will be done using Mcnemar Chi square test for categorical variables and the dependent Student t test for continuous variables. In determining predictors of the outcome variables, independent variables that have a p value of less than 0.2 on bivariate analysis will be entered into the logistic regression model. The result of the logistic regression analysis will be reported using adjusted odds ratio and 95% confidence interval and the level of statistical significance will be determined by a p value of <0.05.

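### For the effect of physical impairment (secondary objective 6), choosing covariates by p<0.2 alone allows, and does not prevent, adjustment for stigma, a consequence of impairment on the protocol's own account

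*Protocol*

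**What the plan says.** The Data management section of the protocol introduces its regression with the words "In determining predictors of the outcome variables". The entry rule is that "independent variables that have a p value of less than 0.2 on bivariate analysis will be entered into the logistic regression model". On output it says: "The result of the logistic regression analysis will be reported using adjusted odds ratio and 95% confidence interval". It lists no candidate variables, names no forced variables and makes no exception for any type of variable.

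Two secondary objectives concern determinants of mental health. Objective 5 is "To determine the effect of socio-demographic variables on mental health status (depression and GAD) status of persons affected by leprosy or BU". Objective 6 is "To determine the effect of physical impairment on mental health status (depression and GAD) of persons affected by leprosy/BU". The other quantitative tests in Data management (chi-square, t, McNemar, paired t) are described for comparing the groups or before with after. The logistic model is therefore the natural place for objectives 5 and 6, although the protocol does not make that link explicitly.

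On mechanism, the Methodology section states: "Persons with leprosy and BU related disabilities are faced with varying degrees of stigma and discrimination which predispose them to mental health problems especially depression". Section 2.5.6 (Data collection methods) includes "Stigma perception among persons affected by leprosy/BU using SARI Stigma scale" among the data to be collected from the same participants.

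**The concern.** A p-value screen asks one thing of a variable: is it associated with the outcome? A confounder and a consequence of the exposure both answer yes, but they need opposite treatment. Adjusting for a confounder removes bias. Adjusting for a consequence of impairment that itself raises the risk of depression removes part of the effect that objective 6 sets out to measure.

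Stigma is the clearest case, because the protocol describes it as following from disability and leading to depression, and measures it. WHOQOL-BREF, WEMWBS and the other symptom scale (GAD-7 in the depression model, PHQ-9 in the GAD model) raise the same problem, since impairment may affect them too.

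At stake is a report that impairment has little or no independent effect, when it may act by the very route the protocol describes. Forcing impairment into the model does not cure this. Only the choice of adjustment variables does.

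**Working it through.** The protocol gives no figure to reproduce here, so this is an illustration of size under stated assumptions.

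**Inputs from the protocol.** Outcome prevalence 50% and N = 400 (Sample size calculation); visible deformity 14-15% of notified leprosy cases (Methodology), used as the lower end for impairment.

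**Assumptions, not in the protocol.** Impaired share 15% to 40%; impairment raises standardised stigma by a = 0.5 to 0.8 SD; odds ratio 1.8 to 2.5 per SD of stigma; direct impairment odds ratio 1.3 or 1.0; clustering ignored.

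**Model.** Let X be impairment (0 or 1) and M = aX + Z, with Z standard normal. Then logit P(Y=1) = b0 + ln(OR_direct)·X + ln(OR_M)·M, with b0 set so that overall prevalence is 50%.

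- With M in the model, the impairment odds ratio is OR_direct, whatever a is.
- With M left out, it is the total odds ratio [p1/(1−p1)] / [p0/(1−p0)], where p1 and p0 are the risks in impaired and unimpaired people averaged over Z.

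**One case worked through.** Take 15% impaired, a = 0.5, OR_M = 1.8 and OR_direct = 1.3. Averaging over Z gives p1 = 0.608 and p0 = 0.481. Check on prevalence: 0.15 × 0.608 + 0.85 × 0.481 = 0.500. Total odds ratio: (0.608/0.392) / (0.481/0.519) = 1.551/0.927 = 1.67. The model containing stigma targets 1.30.

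**Range.** The impaired share (15% to 40%) hardly changes these results.

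| Direct OR | a (SD) | OR per SD of stigma | Total OR, stigma left out | OR, stigma entered |
|---|---|---|---|---|
| 1.3 | 0.5 | 1.8 | 1.67 | 1.30 |
| 1.3 | 0.8 | 2.5 | 2.33 | 1.30 |
| 1.0 | 0.5 | 1.8 | 1.31 | 1.00 |
| 1.0 | 0.8 | 2.5 | 1.86 | 1.00 |

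**Would stigma pass the screen?** In simulated samples of 400 with an odds ratio of 1.5 to 2.0 per SD, stigma had bivariate p<0.2 in 99-100% of samples.

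**Would impairment itself pass?** Not always. With 15% impaired and an odds ratio of 2.0 per SD of stigma, the screen dropped impairment in 15% of samples when its total odds ratio was 1.97, and in 55% when it was 1.37.

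**No mediation (a = 0).** With a direct odds ratio of 1.5 and 2.0 per SD of stigma, leaving stigma out gives 1.44 and entering it gives 1.50. This gap is non-collapsibility of the odds ratio, so a difference between the two odds ratios does not measure mediation.

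**The case against.** The strongest reply is that the protocol never says SARI is an independent variable in this model. The determinants named in its objectives are socio-demographic variables and physical impairment. SARI appears as a baseline and post-intervention measure, and self-stigma as something the self-help groups are meant to reduce. If only the variables in objectives 5 and 6 are candidates, the stigma problem does not arise. A candidate list is also ordinary SAP content. This stands, and it rules out the stronger reading that a reader might infer, namely that the plan does adjust impairment for stigma and so must answer objective 6 wrongly. It does not remove the point about the rule itself, which the protocol does fix: entry depends on the p-value alone, with no safeguard.

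Three further replies have some force.

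- Methodology speaks of stigma and discrimination, not of self-stigma, and the Sample size calculation section names disfigurement and stigma side by side. It would therefore be too strong to say that the protocol names self-stigma as the route. SARI is, however, the participant-level stigma measure collected.
- Objective 6 does not say total or direct effect, and Data management speaks of predictors. An unqualified effect most naturally means the whole effect. If the direct effect is wanted, that should be chosen openly and not left to a screen.
- The bivariate step yields an impairment association not adjusted for stigma. That association is also unadjusted for age, sex, disease and LGA, and the regression result named for reporting is the adjusted odds ratio.

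The effect sizes in the illustration are assumptions, and N = 400 counts leprosy patients only, while all eligible Buruli ulcer patients are added.

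**Conclusion.** The point holds as a weakness of method. Selection by p<0.2 is a poor way to build the model for objective 6, because it allows, and does not prevent, adjustment for consequences of impairment. The result is conditional: if SARI is a candidate it will almost certainly be entered, and the impairment odds ratio then estimates only the part of the effect not running through stigma. The ranges above show how large that loss could be. They rest on the assumed stigma shift, odds ratio per SD and direct odds ratio. The direction needs only that impairment raises stigma and stigma raises depression, as Methodology describes.

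This concerns a secondary, observational objective. The primary objective and the comparison of intervention with control LGAs are untouched. The change is worth making because it is cheap and the possible misreport is material to objective 6.

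**What to change.** For objective 6, replace the p<0.2 rule in Data management (or in the SAP) with one pre-specified logistic model per outcome, depression and GAD:

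- Keep impairment in whatever its p-value.
- Adjust for variables that precede impairment: age, sex, disease (leprosy or Buruli ulcer) and LGA.
- Leave out SARI, WHOQOL-BREF, WEMWBS and the other symptom scale.
- If employment, income or marital items are collected, decide in advance whether each precedes impairment, and adjust only for those that do.

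If a second model adding SARI is reported, label its impairment odds ratio as the association not running through stigma. Do not present the difference between the two odds ratios as the mediated part.

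The cost is a change of wording and at most one extra model per outcome, with no new data. The small downside is that the adjustment set has to be justified on causal grounds before the analysis.
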